8.4 Equipment

- **Cosmed K4B² Metabolic unit.** Cosmed K4B² (K4B2 Cosmed, Italy) is a portable gas analysis system that measures oxygen consumption (VO₂) and Carbon-dioxide production (VCO₂) in a breath by breath fashion. K4B² system consists of a portable unit and battery pack that weight about 2.4 lbs (1100 gm). The portable unit has O₂ and CO₂ analyzers that are bi-directionally connected to a flowmeter and turbine attached to a rubber facemask that is tightly strapped over subject's nose and mouth. K4B² requires calibration before every testing session due to usage of heated sensors for measurements. Manufacturer's recommend at least 45 minutes warm up time for unit under ambient temperature (ideally at 20°C) before calibration. K4B² calibration involves verifying flowmeter and concentrations of gases with labeled concentrations. K4B² acquires heart rate using a telemetric heart rate sensor that is strapped over subject's thorax. The K4B² and battery pack can be securely placed in slots on a standard harness worn by subject. This harness allows access to buttons on the unit on upper back and minimal interference to activities like walking. Data extraction and processing is carried using K4B² custom software.
- **Electromyography (EMG):** Muscle activity will be collected from subjects by electrodes placed upon the skin over lower extremity muscles and also on the lower back muscles. This will be collected during the six-minute walk test.
- **Postural measurement (using EMG):** Muscle activity will be collected from subjects by electrodes placed upon the lower back muscles , upper extremities and lower extremities to measure the posture with each device.
- **Grip and forearm strength load** – Specialty gloves and load cells will be used to measure to amount of load participants are using when using each device on the hands

PROTOCOL TITLE: Life Walker vs. Conventional Rollator and Predicate Mobility Device

and also on the forearm. This will be collected during the six-minute walk test.

- **Activity monitors** will be placed on the body or walker to collect body movement data.
- **HR/BP:** Subjects will wear a heart rate monitor during the study and blood pressure will be taken periodically with a standard BP cuff.

8.5 Clinical Testing

- **10 METER TIMED WALK (10mWT):** This test will examine the patient's gait speed. Patients will be directed to walk at a self-selected speed and at their preferred maximum but safe speed. Patients will be positioned 1 meter before the start line and instructed to walk the entire distance and past the end line approximately 1 meter. The distance before and after the course are meant to minimize the effect of acceleration and deceleration. Time will be recorded using a stopwatch and recorded to the one hundredth of a second (ex: 2.15 sec). The test will be recorded 3 times each, with adequate rest in between. The average of the 3 times should be recorded. Participants will complete the 10mWT 6 times with each device: *3 times Self-selected; 3 times Fast-walking*
- **6 MINUTE WALK TEST (6MWT):** The 6 minute walk test is performed as an objective evaluation of functional exercise capacity. The 6minute walk test is easy to administer, well tolerated, and typically reflective of activities of daily living. The test measures the distance that the patient can walk on a flat, hard surface, indoors, in a period of 6 minutes. The walk test is patient self-paced and assesses the level of functional capacity. Patients are allowed to stop and rest during the test, however, the timer does not stop. If the patient is unable to complete the time, the time stopped is noted and reason for stopping prematurely is recorded. We will record the number of stops and stumbles during the test. This test will be administered while wearing a mask to measure oxygen consumption in addition to blood pressure, heart rate and oxygen saturation.
- **TALKS WHILE WALKING TEST (TWWT Dual Task Test) :** The TWWT is used to determine the effects of cognitive attentional demands during walking by

PROTOCOL TITLE: Life Walker vs. Conventional Rollator and Predicate Mobility Device

introducing a secondary thinking and talking task, while walking. Participants will perform the following tasks, timed walking up to 50 meters, performing a thinking and talking (numerical and/or vocabulary) task while sitting and a dual task while walking (i.e. performing a thinking and talking task while walking). Participants voice will be recorded when performing all the thinking and talking tasks

- **GAITRITE DATA CAPTURE:** The GAITRite system automates measuring temporal and spatial gait parameters via an electronic walkway connected to a computer. The GAITRite electronic walkway contains sensor pads encapsulated in a carpet to collect gait information. The system can be laid over any flat surface. The GAITRite electronic walkway for the study shall be a minimum of 14 feet long. The GAITRite data capture was chosen as measurement of the patient's overall gait quality. Patients will be asked to walk at a self-selected speed across the GAITRite electronic walkway. GAITRite. Participants will complete the GAITRite 6 times with each device: *3 times Self-selected; 3 times Fast-walking*
- **OUTDOOR AMBULATION:** All participants will complete a structured outdoor course of straight walkway, ramps, and a standard side walk with curbs as well as a crosswalk. Time and RPE will be measured.
- **DYNAMIC GAIT INDEX (DGI).** The DGI is clinical test that assesses the individual's ability to modify balance while walking with the walkers in the presence of external demands (i.e. demands like, level walking, look up and down, left and right while walking, stepping over and walking around obstacles and cones).

8.6 Self-Report Questionnaires

- **MODIFIED FALLS EFFICACY SCALE (mFES):** The mFES is self-report questionnaire consisting of 14 items which is designed to measure fear of falling in the elderly. It assesses an individual's perception of balance during activities of daily living by asking "how confident are you that you can do the following activities without falling."
- **MODIFIED FATIGUE IMPACT SCALE (mFIS):** The mFIS is a 21-item short version of perceived impact of fatigue on the subscales of physical, cognitive, and psychosocial functioning.

PROTOCOL TITLE: Life Walker vs. Conventional Rollator and Predicate Mobility Device

- **THE QUEBEC USER EVALUATION OF SATISFACTION WITH ASSISTIVE TECHNOLOGY (QUEST)** was designed to measure the level of satisfaction attribute to assistive technologies. It does so using 27 variables which are scored in terms of perceived importance and satisfaction.
- **VISUAL ANALOG PAIN SCALE (VAS):** The Visual Analog Scale Pain Scale is a measure of perceived pain intensity. It consists of a horizontal line that is 10 centimeters long. On either side of the line is a description of pain- to the left the description will read “No pain,” and to the right the description will read “worst pain imaginable.” The individual is instructed to mark a point on the continuum which represents his/her pain.
- **QUEBEC BACK PAIN DISABILITY Scale:** The back pain scale is a self-report measure that evaluates a patient’s functional status related to back pain.
- **BORG RATE OF PERCEIVED EXERTION:** 6-20 item scale that measures perceived exertion during activity.
- **USER FUNCTIONAL RATING SCALE:** Is specifically to assess the user’s perception of difficulty in performing the functional tasks when using the different assistive devices. The scale is similar to the patient specific functional scale wherein functional tasks are rated in level of their difficulty from “0” (“inability to perform the task”) to “10” (“no difficulty in performing the task.”).
- **Brief Pain Inventory:** This scale is a 9-item self-report measure of measure of perceived pain intensity at different body parts in the past 24 hours.
- **Rosenberg’s Self-Esteem Scale :**

The Rosenberg Self-Esteem Scale is a 10-item self-report measure of global self-esteem. It consists of 10 statements related to overall feelings of self-worth or self-acceptance. The items are answered on a four-point scale ranging from strongly agree to strongly disagree

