8.0 Procedures Involved

Participants will come to the laboratory for a screening and informed consent. Once written consent is obtained, participants will be screen for inclusion eligibility.

Screening/Baseline Procedures

- Informed Consent
- Medical history-Complete medical and surgical history, medications
- Demographics-Age, gender, race, ethnicity
- Review subject eligibility criteria
- Testing sessions will take place over the course of 1-32 days and include the following clinical objective outcome measures, subjective self-report measures and metabolic measures listed.

Overall Sessions:

- Session 1 will include, (i) Consent (ii) Some Self reported measures (baseline) and (iii) Indoor Gait assessment tests with or without metabolics (depending on equipment availability)
- Session 2 will include, (i) Outdoor ambulation, (ii) Indoor gait assessment with or without metabolics (depending on equipment availability), and (iii) Self reported measures
- Session 3 will include, any items that were not completed in session 1 or 2.

▪ Life Walker Upright Training Procedures

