8.1 Walker Training procedures

All participants will be trained on the use of the Life Walker and standard Rollator for a time of 15 min. After training all the testing will be begin.

8.2 Walker Testing procedures: *Experimental order of which walker is used first, second and third during the testing will be randomized using a random number generator.*

PROTOCOL TITLE: Life Walker vs. Conventional Rollator and Predicate Mobility Device

8.3 Overview: Participants will first complete a series of gait testing. Gait testing will include metabolic testing using the K4B2, load and grip testing using load sensors and upper extremity and spine muscle electromyography (EMG) testing. Participants will also be asked to be videotaped during their training sessions. After all the testing is complete, participants will be asked to complete a set of self-report questionnaires. During each device session, participant heart rate, blood pressure and blood oxygenation will be measured. All of these procedures will be repeated with each device.

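### If given per device, as 8.3 reads, a 24-hour pain scale and a global self-esteem scale separate the devices poorly; Aim 2 needs a current-pain VAS marked before and after each device

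*Protocol*

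**What the plan says.** Aims 2 and 3 (section 1.1) are laboratory comparisons of the Life Walker with a rollator and a predicate device, on self-reported pain and on quality of life. Aim 3 gives better self-esteem as the reason to expect a benefit.

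On when questionnaires are given, section 8.3 says: "After all the testing is complete, participants will be asked to complete a set of self-report questionnaires". It then says: "All of these procedures will be repeated with each device". It names no scale and exempts none. Section 8.0 puts "Some Self reported measures (baseline" in session 1 without naming them, and lists self-reports again in session 2.

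On what the scales measure, section 8.6 describes the Brief Pain Inventory thus: "This scale is a 9-item self-report measure of measure of perceived pain intensity at different body parts in the past 24 hours". It describes the Rosenberg scale as a 10-item measure of global self-esteem. The pain VAS asks for a mark on a 10 cm line, with no recall period and no stated moment of marking.

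On device order and spacing, section 8.2 says: "Experimental order of which walker is used first, second and third during the testing will be randomized". Section 8.0 says: "Testing sessions will take place over the course of 1-32 days". No minimum gap between devices is set.

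**The concern.** A device contrast needs a measure that responds to the device just used. The Brief Pain Inventory, as described, asks about a whole day, most of which is spent off the tested device. If two or three devices are used on one day, each rating also takes in the devices used before it. The Rosenberg scale, as described, asks about overall self-worth and refers to no device or recent period, yet it is the only self-esteem measure listed for an aim that rests on self-esteem.

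If these scores are used to compare devices, a finding of no difference could mean that the devices do not differ or that the scale could not show it. The VAS is better placed to measure pain on each device. As described, however, it is not worded for current pain, and no mark is planned before each device, so pain carried over from an earlier device cannot be separated from pain caused by the present one.

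**Working it through.** The protocol states no figure on this point, so there is none to reproduce. The check has three parts.

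**1. Do devices share a day?** This is likely but not stated.
- For: section 8.0 schedules the outdoor course only in session 2 ("Session 2 will include, (i) Outdoor ambulation, (ii) Indoor gait assessment with or without metabolics"), and 8.3 repeats procedures with each device. Session 3 is for unfinished items, and 15.2 treats three sessions as a contingency. With three devices and two sessions, at least two devices must share a session.
- Against: testing may spread over 1 to 32 days, and 8.3 also says: "During each device session, participant heart rate, blood pressure and blood oxygenation will be measured". That could mean a separate session for each device.

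**2. How far do successive 24-hour windows overlap?** For ratings g hours apart, overlap = (24 − g)/24. The gaps are assumed.

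| g (hours) | 1 | 2 | 4 | 8 | 24 or more |
|---|---|---|---|---|---|
| Overlap | 96% | 92% | 83% | 67% | 0% |

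With no overlap, one device still fills only h/24 of the window. The only exposure time in the protocol is the 15 minutes of training in 8.1: 0.25/24 = 1.0%. An assumed 0.5 to 3 hours on a device gives 2.1% to 12.5%.

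**3. How much of a true difference survives?** Let pain be a on the Life Walker and b on each of two equally painful comparators, with a < b. Average over the 6 device orders, and let each score take in devices used earlier that day. The recall rule and the hours h per device are assumptions.

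*Worst-pain recall, with pain before the visit no worse than on the devices.* A comparator always scores b.
- Three devices on one day: the Life Walker scores a only when it is first (2 of 6 orders), so the contrast is (b − a)/3, or 33%.
- Two on one day: the Life Walker is affected only as the second of that pair (2 of 6 orders), so 67% is kept.
- Separate days: 100%.

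An assumed true difference of 2 points would show as 2 × 1/3 = 0.7, 2 × 2/3 = 1.3, or 2.0 points.

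*Time-average recall.* The share kept is (h/24) × (1 − p), where p is the chance that a given other device was used earlier that day: 1/2 with three on one day, 1/6 with two, 0 on separate days.

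| | Three on one day | Two on one day | Separate days |
|---|---|---|---|
| h = 1 | 2.1% | 3.5% | 4.2% |
| h = 2 | 4.2% | 6.9% | 8.3% |

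No such calculation is possible for the Rosenberg scale. There the point rests on its description alone, since the protocol gives no data on responsiveness.

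**The case against.** The strongest reply is that the per-device reading is one of two. Section 8.3 speaks of a set, which need not be every scale in 8.6. Section 8.0 makes some self-reports baseline, and a 24-hour scale and a global self-esteem scale are natural candidates. No passage names the Brief Pain Inventory as the Aim 2 measure, and linking scales to aims is commonly left to a statistical analysis plan. This stands: the point is conditional. If both scales are meant as baseline only, what remains is the unreconciled wording of 8.0 and 8.3 and the unfixed VAS.

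The reply also rightly limits several stronger inferences that a reader might draw:
- *That current pain would never be captured.* On the same reading of 8.3, the VAS is repeated with each device. Its wording and timing need fixing; the measure is not absent.
- *That the scales cannot detect a device effect at all.* Under worst-pain recall on separate days, the model above loses nothing. Poorly sensitive is as far as the text goes.
- *That the comparison is biased.* Device order is randomised, so the main effect is dilution and carryover.
- *That Aims 2 and 3 fail.* The VAS, QUEST and the User Functional Rating Scale can still separate devices.
- *That Aim 3 should be rebuilt on QUEST and the User Functional Rating Scale.* These measure satisfaction and task difficulty. That would change the aim and is the sponsor's design choice.

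Lastly, the Brief Pain Inventory is the only listed scale described as recording pain by body part. That bears on a walker whose forearm supports are meant to relieve load (section 2.0), so making it baseline only has a real cost.

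**Conclusion.** The point holds in conditional form. If the Brief Pain Inventory and the Rosenberg scale are given per device, as 8.3 reads, they are poorly suited to telling short laboratory exposures apart, and a null result on either would say little about the devices.

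The size cannot be pinned down. The 2% to 100% range depends on assumed recall rules, hours per device and spacing. The firmer result is the overlap: for same-day ratings up to 4 hours apart, at least 83% of the recall window is shared.

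This is worth correcting before data are collected. Later analysis cannot supply a before-device mark that was not taken, nor change the wording under which a VAS mark was made. It is a cheap gain in measurement for Aim 2 and for the self-esteem part of Aim 3. It does not affect the primary gait objective.

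**What to change.** - **Aim 2.** Make the VAS, worded for pain at this moment, the device contrast. Have it marked immediately before and immediately after each device's testing, and use the before-mark to account for pain carried over from earlier devices.
- **Brief Pain Inventory.** Do not use the 24-hour score to compare devices. Keep it at baseline or, if pain by body part is wanted per device, reword its recall to the device just used.
- **Rosenberg scale.** Treat it as a baseline descriptor, or state in advance that a null per-device result is not evidence of no device effect.
- **Sections 8.0 and 8.3.** Align them by marking each scale in 8.6 as baseline only or per device.

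**Cost.** There are 3 × 2 = 6 VAS marks per participant instead of 3, so about three more. This assumes one block of testing per device; if a device's tests are split over sessions, the pair must be repeated or tied to one named session.

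Making both scales baseline only leaves 9 + 10 = 19 items. The saving is 0 if that is already the intent, 3 × 19 − 19 = 38 if they are now per device, and 4 × 19 − 19 = 57 if they are now both baseline and per device.

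What is lost is a 24-hour pain score by device and, if the Rosenberg scale becomes baseline only, a self-esteem score by device. In that case the self-esteem expectation in Aim 3 is not tested by device. Pain by body part is also lost per device unless the reworded version is used.

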9.0 Data Management

PROTOCOL TITLE: Life Walker vs. Conventional Rollator and Predicate Mobility Device

- 9.1 Subjects' records will be kept completely confidential:** Every possible precaution will be taken to protect the privacy interests of subjects. To begin with participation in this is completely voluntary. Trained research personnel will explain the purpose of the study and intended use of subject's personal health information and precautions taken to keep the study information and data confidential. Data will be collected and kept confidential and compliant with HIPAA requirements. Research data will be de-identified and stored in locked cabinets in the lab with access only to research staff. Electronic data will be de-identified and kept on secure, password protected files and password protected computers of RIC. Only authorized research personnel will have access to the study related data.
- 9.2 Record Retention:** Study documentation will be collected and kept confidential and compliant with HIPAA requirements. Data will be held for 3 years after the study is completed and published.

10.0 Withdrawal of Subjects*

- 10.1** Patient voluntarily withdraws
- 10.2** Patient withdraws consent (termination of treatment and follow-up);
- 10.4** Patient is unable to comply with protocol requirements
- 10.5** Patient demonstrates change in medical condition
- 10.5** Patient experiences adverse event that makes continuation in the protocol unsafe;
- 10.6** PI judges continuation in the study would not be appropriate;

11.0 Risks to Subjects*

- 11.1** There is a risk of falling during training and testing. The risk of falling will be reduced by having each participant supervised during training and testing by a trained research professional in all testing procedures and fully trained in device use. During testing and training, the participant will use a gait belt for safety. Each participant will be educated in the safe use of the device and will demonstrate safe use with assistive devices, as necessary. The risk is similar to that during any clinical outpatient physical therapy session.
- 11.2** There is a risk of muscle soreness due to increased physical activity during training and testing sessions. All subjects will work with trained research staff. Adequate rest will be given and subjects will be monitored by the researchers for verbal or visual signs of fatigue or discomfort.

PROTOCOL TITLE: Life Walker vs. Conventional Rollator and Predicate Mobility Device

- 11.3** There is a risk of skin irritation from using the EMG electrode patches. The adhesive is hypo-allergenic. All subjects will be educated in signs and symptoms of skin irritation and we will remove the patches if irritation occurs.

12.0 Potential Benefits to Subjects

- 12.1** There will likely be no direct benefit by participating in this research study. The participants might feel the differences between the devices and be better informed on devices that they may have better preferences for.

13.0 Setting

- 13.1** Procedures will be performed in the clinical laboratory housed in a Rehabilitation inpatient and outpatient hospital.

14.0 Resources Available

- 14.1 Staffing:** The RIC houses the Center for Bionic Medicine (CBM) which is an internationally recognized research center focused on the design, control, and evaluation of multi-function technologies for individuals with disabilities. The CBM is a large, fully equipped facility with a research team of more than 35 staff members including physicians, therapists, neuroscientists, engineers, software developers, graduate students, post-doctoral researchers, and administrative staff that facilitates integration of teaching, research, and clinical knowledge.

All training will involve trained research staff, and will occur in compliance with standard clinical training methods. Subject safety will be paramount at all times; harness systems and clinical oversight will be in place when necessary.

- 14.2 Facilities:** The PI of this study, [name], is Director of the Max Nader Center for Rehabilitation Technologies and Outcomes (MN Center), within CBM at the RIC Hospital. The MN Center has laboratory space of 1000 sq. ft. for clinical evaluation of patients and assessment of ambulation and functional activities. This includes ramps, stairs, parallel bars, and other clinical evaluation equipment. This area is covered by an overhead support system such that a patient can move throughout the room and over obstacles while being safely harnessed in case of a stumble or fall. Adequate dedicated office space is available for private meetings with potential subjects, performing physical evaluations, explaining

PROTOCOL TITLE: Life Walker vs. Conventional Rollator and Predicate Mobility Device

the study protocol and obtaining study consent, performing data analysis, and writing manuscripts.

